#### **11.1.6.2 Reporting Period for Adverse Events**

All AEs regardless of seriousness or relationship to the study drug spanning from the first dose of acalabrutinib until 30 calendar days after discontinuation or completion of study drug, as defined by this clinical study protocol, are to be recorded on the corresponding screen(s) included in the eCRF.

All AEs resulting in discontinuation from the study should be followed until resolution or stabilization. All new AEs occurring during the AE reporting period must be reported and followed until resolution unless, in the opinion of the Investigator, the AE or laboratory abnormality is not likely to improve because of the underlying disease. In this case, the Investigator must record his or her reasoning for this decision in the patient's medical record.

Thirty days or more after completion of protocol-specific treatment or discontinuation, only AEs, SAEs, or deaths assessed by the Investigator as treatment-related are to be reported.

#### **11.1.7 Assessment of Adverse Events**

All AEs and SAEs whether volunteered by the patient, discovered by study personnel during questioning, or detected through physical examination, laboratory test, or other means will be reported appropriately. Each reported AE or SAE will be described by its duration (e.g., start and end dates), regulatory seriousness criteria if applicable, suspected relationship to the study drug (see following guidance), and actions taken.

To ensure consistency of AE and SAE causality assessments, Investigators should apply the following general guideline:

**YES:** There is a plausible temporal relationship between the onset of the AE and administration of the study treatment, and the AE cannot be readily explained by the patient's clinical state, intercurrent illness, or concomitant therapies, and/or the AE follows a known pattern of response to the study drug, and/or the AE abates or resolves upon discontinuation of the study drug or dose reduction and, if applicable, reappears upon re-challenge.

**NO:** Evidence exists that the AE has an etiology other than the study drug (e.g., pre-existing medical condition, underlying disease, intercurrent illness, or concomitant medication), and/or the AE has no plausible temporal relationship to study drug administration (e.g., cancer diagnosed 2 days after first dose of study drug).

#### **11.2 Serious Adverse Event Reporting by Investigators**

Adverse events classified by the treating Investigator as "serious" require expeditious handling and reporting to the Innovations Safety Department in order to comply with regulatory

requirements. Determination of “life-threatening” or “serious” is based on the opinion of either the Sponsor or the Investigator.

Serious AEs may occur at any time from the first dose of acalabrutinib through the 30-day follow-up period after the last dose of study drug. **The Innovations Safety Department must be notified of all SAEs, regardless of causality, within 24 hours of the first knowledge of the event by the treating physician or research personnel.**

To report an SAE, the SAE Report Form should be completed with the necessary information.

The SAE Report Form should be sent to the Innovations Safety Department via fax or e-mail using the following contact information (during both business and non-business hours):

Sarah Cannon Innovations Safety Department  
Safety Dept. [contact]  
Safety Dept. Email: [[contact]](mailto:[contact])

Transmission of the SAE report should be confirmed by the site personnel submitting the report.

Follow-up information for SAEs and information on non-serious AEs that become serious should also be reported to the Innovations Safety Department as soon as it is available; these reports should also be submitted using the Innovations SAE Report Form. The detailed SAE reporting process will be provided to the sites in the SAE reporting guidelines contained in the study reference manual.

### **11.3 Recording of Adverse Events and Serious Adverse Events**

#### **11.3.1 Diagnosis versus Signs and Symptoms**

All AEs should be recorded individually in the patient’s own words (verbatim) unless, in the opinion of the PI or designated physician, the AEs constitute components of a recognized condition, disease, or syndrome. In the latter case, the condition, disease, or syndrome should be named rather than each individual sign or symptom. If a constellation of signs and/or symptoms cannot be medically characterized as a single diagnosis or syndrome at the time of reporting, each individual event should be recorded as an AE or SAE as appropriate on the relevant form(s) (SAE Report Form and/or AE eCRF screen). If a diagnosis is subsequently established, it should be reported as follow-up information is available. If a diagnosis is determined subsequent to the reporting of the constellation of symptoms, the signs/symptoms should be updated to reflect the diagnosis.

Progression of malignancy (including fatal outcomes), if documented by use of an appropriate method (e.g., as per RECIL), should not be reported as an SAE.

#### **11.3.2 Persistent or Recurrent Adverse Events**

A persistent AE is one that extends continuously, without resolution, between patient evaluation time points. Such events should only be recorded once on the SAE Report Form and/or the AE eCRF screen. If a persistent AE becomes more severe or lessens in severity, it should be recorded on a separate SAE Report Form and/or AE eCRF screen.

A recurrent AE is one that occurs and resolves between patient evaluation time points and subsequently recurs. All recurrent AEs should be recorded on an SAE Report Form and/or AE eCRF screen.

### **11.3.3      Abnormal Laboratory Values**

If an abnormal laboratory value or vital sign is associated with clinical signs and/or symptoms, the sign or symptom should be reported as an AE or SAE, and the associated laboratory value or vital sign should be considered additional information that must be collected on the relevant eCRF screen. If the laboratory abnormality is a sign of a disease or syndrome, only the diagnosis needs to be recorded on the SAE Report Form and/or AE eCRF screen.

Abnormal laboratory values will be reported as an AE if: the laboratory result requires an adjustment in the study drug(s) or discontinuation of treatment, and/or laboratory findings require additional testing or surgical intervention, a laboratory result or finding is associated with accompanying symptoms, or a laboratory result is considered to be an AE by the Investigator.

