### **6.5.5 Laboratory Assessments**

Laboratory samples (CBC, clinical chemistry, urinalysis, and virology) are to be collected as outlined in Appendix D. Laboratory results will be graded using NCI CTCAE Version 5.0.

Hematology studies must include CBC with differential including, but not limited to, white blood cell count, hemoglobin, hematocrit, platelet count, ANC, and absolute lymphocyte count.

Coagulation testing will include PT/INR or aPTT.

Serum chemistry will include albumin, alkaline phosphatase, ALT, AST, bicarbonate, blood urea nitrogen (BUN), calcium, chloride, creatinine, glucose, lactate dehydrogenase (LDH), magnesium, phosphate/phosphorus, potassium, sodium, total bilirubin, total protein, and uric acid.

If an unscheduled ECG is done at any time, then an electrolyte panel (e.g., calcium, magnesium, and potassium) must be done to coincide with the ECG testing.

A urinalysis will include pH, ketones, specific gravity, bilirubin, protein, blood and glucose.

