#### **7.5.1.3 Cytopenias**

Treatment-emergent Grade 3 or 4 cytopenias including neutropenia, anemia, and thrombocytopenia have occurred in clinical studies with acalabrutinib. Monitor blood counts as medically appropriate.

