#### **10.4.3 Safety Analysis**

Safety will be assessed through the analysis of the reported incidence of treatment-emergent AEs. Treatment-emergent AEs are those with an onset on or after the initiation of therapy, and will be graded according to NCI CTCAE Version 5.0. A copy of the CTCAE scoring system may be downloaded from:

[https://ctep.cancer.gov/protocolDevelopment/electronic\\_applications/docs/CTCAE\\_v5\\_Quick\\_Reference\\_8.5x11.pdf](https://ctep.cancer.gov/protocolDevelopment/electronic_applications/docs/CTCAE_v5_Quick_Reference_8.5x11.pdf).

The AEs will be coded using the Medical Dictionary for Regulatory Activities (MedDRA) and summarized using system organ class and preferred term for all patients in the Safety Analysis Set. In addition, summaries of SAEs, AEs leading to treatment discontinuation, AEs by maximum NCI CTCAE grade, and AEs related to the study drug will also be presented.

Other safety endpoints including laboratory results, vital signs, ECG findings, and other protocol-specified tests will be listed and/or summarized for all patients in the Safety Analysis Set.

Concomitant medications will be coded using the WHO Drug Dictionary and they will be listed and summarized.

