### **11.1.6 Recording and Reporting of Adverse Events**

#### **11.1.6.1 Recording of Adverse Events**

All AEs of any patient during the course of the research study will be recorded in the eCRF, and the Investigator will give his or her opinion as to the relationship of the AE to the study drug (e.g., whether the event is related or unrelated to study drug administration).

All AEs should be documented. A description of the event, including its date of onset and resolution, whether it constitutes an SAE or not, any action taken (e.g., changes to study drug), and outcome should be provided along with the Investigator’s assessment of causality (e.g., the relationship to the study drug). For an AE to be a suspected TEAE there should be at least a reasonable possibility of a causal relationship between the protocol treatment and the AE. Adverse events will be graded according to the NCI CTCAE Version 5.0, and changes will be documented.

If the AE is serious, it should be reported immediately to the Innovations Safety Department. Other untoward events occurring in the framework of a clinical study are to be recorded as AEs (e.g., AEs that occur prior to assignment of the study drug that are related to a protocol-mandated intervention, including invasive procedures such as biopsies, medication washout, or no treatment run-in).

Any clinically significant signs and symptoms, abnormal test findings, changes in physical examination, hypersensitivity, and other measurements that occur will be reported as AEs and collected on the relevant eCRF screen.

Test findings will be reported as an AE if: the test result requires an adjustment in the study drug(s) or discontinuation of treatment; test findings require additional testing or surgical intervention; a test result or finding is associated with accompanying symptoms; and/or a test result is considered to be an AE by the Investigator.

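### Section 11.3.3 gives two conflicting rules for laboratory abnormalities with symptoms, so cytopenia AE counts may differ between sites

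*Combined protocol and SAP*

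**What the plan says.** Section 11.3.3 has two paragraphs.

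- **Paragraph 1.** When an abnormal value comes with signs or symptoms, it is the sign or symptom that counts as the AE (or SAE). Of the value, the section says: "the associated laboratory value or vital sign should be considered additional information that must be collected on the relevant eCRF screen". A separate sentence covers a value that points to an underlying disease or syndrome; there, "only the diagnosis needs to be recorded on the SAE Report Form and/or AE eCRF screen".
- **Paragraph 2.** The abnormal value is reported as an AE if any of several criteria is met. One is that "the laboratory result requires an adjustment in the study drug(s) or discontinuation of treatment". Another is a need for further testing or surgery. The last two are given as "a laboratory result or finding is associated with accompanying symptoms, or a laboratory result is considered to be an AE by the Investigator".

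Section 11.1.6.1 lists the same kind of triggers for test findings, including that "a test result or finding is associated with accompanying symptoms". It also treats clinically significant abnormal findings as AEs.

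On the risk, section 7.5.1.3 states: "Treatment-emergent Grade 3 or 4 cytopenias including neutropenia, anemia, and thrombocytopenia have occurred in clinical studies with acalabrutinib". On the data, section 6.5.5 states: "Laboratory results will be graded using NCI CTCAE Version 5.0". On the analysis, section 10.4.3 builds its incidence, maximum-grade and discontinuation tables from reported AEs. For the rest it says: "Other safety endpoints including laboratory results, vital signs, ECG findings, and other protocol-specified tests will be listed and/or summarized". It names no worst-grade or shift table.

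**The concern.** One clinical situation can be recorded in two ways, depending on which paragraph a site reads. A low platelet count with bleeding is a bleeding AE under paragraph 1 and also a platelet-count AE under paragraph 2. The protocol itself names this case: section 8.1 lists Grade 3 thrombocytopenia with significant bleeding, and Table 2 has a row for Grade 3 or 4 platelet decrease with bleeding that requires transfusion.

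AE incidence is a secondary objective (section 2.2). The trial is single-arm at about 10 sites, so there is no concurrent arm in which differences in recording habit would cancel. Patients start about 100 days after transplant and may enter with an ANC of 1,000/mm³ and platelets of 75,000/mm³ (section 3.2). Low counts at baseline are therefore allowed, and an AE row alone does not separate on-treatment change from the post-transplant state. Graded laboratory values could provide that check, but a bare listing would satisfy section 10.4.3.

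**Working it through.** The plan states no figure that depends on this point, so there is none to reproduce. The check is a comparison of the rules, followed by an illustration of scale.

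**Step 1. Apply the rules to four kinds of cytopenia.**

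| Case | 11.3.3 paragraph 1 | 11.3.3 paragraph 2 and 11.1.6.1 | Conflict? |
|---|---|---|---|
| Symptoms, and study drug changed | Symptom is the AE; value is supporting data. No exception for a drug change | Value is an AE on two criteria | Yes |
| Symptoms, no drug change | Symptom is the AE; value is supporting data | Value is an AE on the symptom criterion | Yes |
| No symptoms, but drug change or further testing needed | Silent | Value is an AE | No |
| No symptoms, no drug change, no further testing | Silent | AE if the Investigator considers it one | No |

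The contradiction is confined to the first two rows.

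**Step 2. Follow each reading into the tables.** Under paragraph 1 the preferred term is the symptom, so the case may be missing from the cytopenia row. Under paragraph 2 it appears in that row and may appear under the symptom as well. If the tables count patients, the second term does not inflate the cytopenia row, but it does add to the total number of events.

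**Step 3. Illustrate the scale.**

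Inputs: about 50 patients (section 5), and the Grade ≥3 AE rates in the 124-patient relapsed/refractory study described in section 1.5, namely neutropenia 10.5%, anemia 8.9% and thrombocytopenia 4.0%. Let f be the share of cytopenias recorded only under a symptom or other diagnosis. The documents give no value for f, so it is varied over its whole range.

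Formula: expected count in the cytopenia row = 50 × rate × (1 − f). At f = 0 this gives 50 × 0.105 = 5.25, 50 × 0.089 = 4.45 and 50 × 0.040 = 2.0, a total of 11.7 patient-events.

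| f (assumed) | Neutropenia | Anemia | Thrombocytopenia | Total |
|---|---|---|---|---|
| 0 | 5.25 | 4.45 | 2.0 | 11.7 |
| 0.25 | 3.9 | 3.3 | 1.5 | 8.8 |
| 0.50 | 2.6 | 2.2 | 1.0 | 5.9 |
| 0.75 | 1.3 | 1.1 | 0.5 | 2.9 |
| 1 | 0 | 0 | 0 | 0 |

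Totals are computed before rounding. As an arbitrary example, recording 3 instead of 5 neutropenia patients of 50 moves the estimate from 10% (exact 95% CI 3.3 to 21.8) to 6% (1.3 to 16.5).

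The source rates are themselves AE-reported and come from a different population. They show scale only and are not a laboratory benchmark.

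**The case against.** A reader might infer that cytopenias will be undercounted, or that the rates are biased downward. The documents do not support that, for four reasons.

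- Paragraph 2 has criteria that do not depend on symptoms. Table 2 calls for withholding drug for several of the worst cytopenias, so many of these meet the drug-adjustment criterion. This stands in part: it protects the count only where a site applies paragraph 2, because paragraph 1 makes no exception for such cases.
- Section 11.3.1 asks for the recognized condition to be named in place of its component signs and symptoms. Fatigue from anemia can therefore be recorded as anemia. The diagnosis-only sentence can work the same way where the cytopenia is the diagnosis. This stands.
- A site following paragraph 2 loses no cytopenia and may record two terms. This stands, and it means the error has no fixed direction.
- Paragraph 1 still requires the value to be collected, so the data are not lost. This stands, and it is why a laboratory table is feasible.

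A reader might also infer that leaving an asymptomatic Grade 3 value to Investigator judgement is an error. It is a coherent rule that neither paragraph contradicts.

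A further objection is that section 10.4 leaves full analysis detail to the Statistical Analysis Plan, and the wording of 10.4.3 does not rule out a grade table. That is fair for the table. An analysis plan cannot, however, repair a recording rule that sites have already applied differently.

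Nor is the stopping rule in section 3.5 put at risk. A discontinuation caused by a symptomatic cytopenia is due to an AE under either paragraph.

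**Conclusion.** The contradiction within section 11.3.3 is established by the text, and nothing says which paragraph prevails. What follows is that cytopenia AE counts may be inconsistent between sites: possibly understated where paragraph 1 is followed, possibly recorded under both terms where paragraph 2 is followed.

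The size cannot be determined from the documents. The illustration runs from no loss (f = 0) to complete loss (f = 1). It assumes that the cited study's rates apply to 50 treated patients, and any f above 0 means that no other criterion or diagnosis term kept those cases in the cytopenia row.

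This is a safety-reporting point of modest weight. It should be corrected because it touches a secondary objective and a named risk, and because the correction is cheap.

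**What to change.** 1. **Section 11.3.3.** State one rule, aligned with 11.1.6.1: report the sign or symptom, and also report the laboratory abnormality as an AE when it meets any paragraph 2 criterion. State how this fits with the diagnosis-only sentence and with 11.3.1, so that one event is not counted twice under the same concept.
2. **Section 10.4.3.** For hematology and liver tests, replace the open choice between listing and summarizing with a table of worst on-treatment CTCAE grade and shift from the last pre-dose value. Use all scheduled and unscheduled results already collected. Present it beside the AE-reported incidence and not as a substitute, because the stated objective is the incidence of AEs.

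**Cost.** Wording in two sections and one extra table; no new data. Reported cytopenia rates may be higher. The laboratory table can also miss nadirs: under Appendix D clinic visits move from monthly to every 2 months in Cycles 7-12 and every 3 months from Cycle 13, and no CBC is scheduled at the end-of-treatment visit. That limitation should be stated with the table.

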### **11.3.4      Deaths**

Deaths that occur during the protocol-specified AE reporting period that are attributed by the Investigator solely to PD will be recorded on the “End of Study” eCRF screen. All other on-study deaths, regardless of attribution, will be recorded on an SAE Report Form and expeditiously reported to the Innovations Safety Department.

When recording an SAE with an outcome of death, the event or condition that caused or contributed to the fatal outcome should be recorded as the single medical concept on the SAE Report Form and AE eCRF screen. If the cause of death is unknown and cannot be ascertained at the time of reporting, record “Death NOS” (“death cause unknown”) on the AE eCRF screen. During post-study survival follow-up, deaths attributed to PD will be recorded on the “Follow-up Summary” and “Death Page” eCRF screens.

### **11.3.5      Hospitalization, Prolonged Hospitalization, or Surgery**

Any AE that results in hospitalization of >24 hours or prolongation of pre-existing hospitalization should be documented and reported as an SAE unless specifically instructed otherwise in this protocol. There are some hospitalizations that do not require reporting as an SAE.

Treatment within or admission to the following facilities is not considered to meet the criteria of “inpatient hospitalization” (although if any other SAE criteria are met, the event must still be treated as an SAE and immediately reported):

- Emergency department or emergency room
- Outpatient or same-day surgery units
- Observation or short-stay unit
- Rehabilitation facility
- Hospice or skilled nursing facility
- Nursing homes, custodial care, or respite care facility

Hospitalization during the study for a pre-planned surgical or medical procedure (one which was planned prior to entry in the study) does not require reporting as an SAE.

#### **11.3.6 Pre-Existing Medical Conditions**

A pre-existing medical condition is one that is present at the start of the study. Such conditions should be recorded on the General Medical History eCRF screen. A pre-existing medical condition should be recorded as an AE or SAE only if the frequency, severity, or character of the condition worsens during the study. When recording such events on an SAE Report Form and/or AE eCRF screen, it is important to convey the concept that the pre-existing condition has changed by including applicable descriptors.

#### **11.3.7 New Cancers**

The development of a new primary cancer should be regarded as an AE, with the exception of early non-melanoma cancers, and will generally meet at least one of the seriousness criteria (see Section 11.1.2). New primary cancers are those that are not the primary reason for the administration of the study drug and have developed after the inclusion of the patient in the study. They do not include metastases of the original cancer. Symptoms of metastasis or the metastasis itself should not be reported as an AE/SAE, as they are considered to be PD.

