## 5. STUDY DESIGN

This is a single arm, multi-center, Phase II study of subjects with MCL who will receive acalabrutinib as maintenance therapy post-BMT. In general, subjects will provide informed consent prior to BMT to collect the required central labs. However, a limited number of subjects may be allowed to provide informed consent following BMT, determined on a case-by-case basis by the Principal Investigator (PI). In this event, any of the study assessments required prior to BMT not performed for standard of care will not be required.

Subjects will undergo a standard of care BMT with conditioning regimen determined by the treating physician per institutional guidelines. The BMT is not considered part of this study. Following completion of the BMT, a second screening will begin between Day 80 and Day 100. Maintenance therapy with acalabrutinib will begin on Day 100 in 28-day cycles. Subjects will self-administer 129 mg acalabrutinib BID until they reach 2 years post-BMT (approximately 22 cycles). Subjects who experience PD while on study will be encouraged to provide a fresh biopsy to assess lymphoma genome alterations. All subjects will be followed for up to 5 years post-BMT for PFS.

Approximately 50 subjects are planned to be enrolled after receiving BMT.

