#### **7.5.1.4 Second Primary Malignancies**

Events of second primary malignancies, including non-skin carcinomas, have been reported in clinical studies with acalabrutinib. The most frequently reported second primary malignancy was skin cancer.

Subjects with a second primary malignancy should be managed according to institutional guidelines with maximal supportive and therapeutic care and diagnostic evaluations as clinically indicated.

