- n. Patients with a known history of hepatitis C virus (HCV) or who are hepatitis C antibody positive should be tested for HCV RNA during screening. No further testing beyond screening is necessary if PCR results are negative, except if clinically indicated (see Section 6.5.6).
- o. If not obtained during Screening #1 (prior to BMT)
- p. Collect a fresh lymphoma biopsy at disease progression
- q. **MRD analysis with blood sample:** Collect a blood sample prior to beginning maintenance on Day +100 (Screening #2), 6 months (~Cycle 4 Day 1), 1 year (~Cycle 10 Day 1) and 2 years post-BMT (~Cycle 22 Day 1).
- r. **MRD analysis with bone marrow biopsy and aspirate:** Collect a bone marrow biopsy and aspirate prior to beginning maintenance on Day +100 (Screening #2) and at 1 year post-BMT (~Cycle 10 Day 1).
- s. CT/MRI/FDG-PET scans will be done post-BMT (Day 80-100), at 6 months, 12 months, 18 months and 24 months. Thereafter, scans will be done per institutional standard operating procedures.
- t. Record all AEs regardless of seriousness or relationship spanning from the first dose of acalabrutinib until 30 calendar days after discontinuation or completion of study drug.
- u. Coagulation testing will include PT/INR or aPTT.

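### Section 11.3.7 exempts early non-melanoma cancers from AE recording, so second primary malignancy, a named risk, would be undercounted; the sections on the AE window also need reconciling

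*Combined protocol and SAP*

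**What the plan says.** **The risk.** Section 7.5.1.4 states: "Events of second primary malignancies, including non-skin carcinomas, have been reported in clinical studies with acalabrutinib". It adds: "The most frequently reported second primary malignancy was skin cancer".

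**The rule for new cancers.** Section 11.3.7 reads: "The development of a new primary cancer should be regarded as an AE, with the exception of early non-melanoma cancers". It does not define early, and the word skin does not appear.

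**The AE window.** Appendix D footnote t records all AEs, whatever their relationship to the drug, "spanning from the first dose of acalabrutinib until 30 calendar days after discontinuation or completion of study drug". Section 11.1.6.2 sets the same period. From then on, it says, "only AEs, SAEs, or deaths assessed by the Investigator as treatment-related are to be reported". Two other sections use wider language. Section 6.5.11 collects AEs from consent for as long as the patient takes part, and mentions the 30 days after the last dose as included. Section 11.1.6.1 records all AEs that occur while the study runs.

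**Follow-up.** Section 5 states: "All subjects will be followed for up to 5 years post-BMT for PFS". Section 6.4.6 lists two items for the 3-monthly contacts from 2 years post-BMT: a biopsy at progression and PFS status. Appendix D footnote h lets a telephone call replace the visit.

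**The concern.** AE incidence is a secondary objective (Section 2.2). Patients in remission after transplant take a drug for up to about 22 cycles that the protocol itself links to second cancers. A reader of the safety results would expect the count of new cancers to be complete, at least while AEs are being recorded in full.

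Section 11.3.7 prevents that. It takes a group of new cancers out of the AE definition, and the group overlaps the risk described in Section 7.5.1.4. Because its boundary is unclear, two sites could handle the same cancer differently. The window is a second, separate gap. Patients are contacted for years after the drug stops, but no section lists a question about new cancers at those contacts.

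**Working it through.** The documents give no second-cancer rate, no share of cancers that would be exempt, and no share that would be judged related. The plan therefore has no figure of its own to reproduce. The check is a comparison of rules, followed by day arithmetic.

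**Step 1: which cancers the exception removes during full AE recording.**

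| New primary cancer | 11.3.7 as printed | 11.3.7 if skin was meant | 11.1.1 alone |
|---|---|---|---|
| Early non-melanoma skin cancer | exempt | exempt | AE |
| Early colon, breast, lung or prostate cancer | exempt | AE | AE |
| The same cancers when not early | AE | AE | AE |
| Melanoma | AE | AE | AE |

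Either reading exempts at least one row that the general definition would count. Section 7.5.1.4 says only that skin cancer is most frequent, without splitting it by type or stage, so the exempt share is unknown.

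**Step 2: whether another route restores the exempt cases.** The list of AEs of special interest (Section 11.1.5) contains only ventricular arrhythmias. The safety analysis (Section 10.4.3) describes no summary of new cancers. Section 10.4 leaves full detail to the SAP, but a table can show only what was recorded.

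**Step 3: the window for one patient.** Inputs:
- First dose is Day 100 (Section 5: "Maintenance therapy with acalabrutinib will begin on Day 100 in 28-day cycles").
- Drug ends at 2 years: 2 × 365.25 = Day 730.5.
- Full AE recording ends 30 days later: Day 760.5.
- Follow-up ends at 5 years: 5 × 365.25 = Day 1,826.25.

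Results:
- Full recording: 760.5 − 100 = 660.5 days.
- Related-only reporting: 1,826.25 − 760.5 = 1,065.75 days.
- Total: 1,826.25 − 100 = 1,726.25 days.
- Related-only share: 1,065.75 / 1,726.25 = 61.7%.

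If the drug stops on day s post-BMT for a reason other than progression, and the patient stays in follow-up to 5 years, the share is (1,826.25 − s − 30) / 1,726.25. It is 72%, 83% and 93% for stopping at 18, 12 and 6 months.

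**Step 4: person-time, allowing for progression and death.** Assume 50 patients, a constant hazard λ = −ln(S)/2 from first dose, where S is 2-year PFS, and drug taken to 2 years unless PFS ends first. Let a = 660.5/365.25 = 1.808 years and b = 1,726.25/365.25 = 4.726 years. Then:
- full recording = 50 × (1 − e^(−λa)) / λ
- related-only = 50 × (e^(−λa) − e^(−λb)) / λ

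| 2-year PFS | Source | λ | Full recording, person-years | Related-only, person-years | Related-only share |
|---|---|---|---|---|---|
| No attrition | reference | 0 | 90.4 | 145.9 | 61.7% |
| 80% | Section 10.2 planning value | 0.1116 | 81.9 | 101.8 | 55.4% |
| 76% | rituximab-maintenance study quoted in Section 1.3 | 0.1372 | 80.1 | 93.8 | 53.9% |

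**The case against.** The strongest reply is that the exception is a slip for non-melanoma skin cancers. Exclusion criterion 4 in Section 3.3 already sets aside treated basal and squamous cell skin cancers, which makes that reading likely. It narrows the problem but does not remove it: the text still needs correcting, and part of the most frequent type would still go unrecorded.

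A second reply is that other rules pull towards capture. Section 11.1.1 counts any untoward medical occurrence, and Section 11.1.6.1 makes a test finding an AE if it needs further testing or surgery. This stands in part. A reader might infer that early cancers would necessarily skip SAE reporting, and the documents do not support that, because a site could reach the SAE route through these general rules. What they show is a conflict between a specific exception and general definitions.

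A third reply concerns the window. Sections 6.5.11 and 11.1.6.1 can be read as wider than 30 days, and Section 6.5.2 mentions a physical examination at long-term visits. The 30-day text is more specific, and neither Section 6.4.6 nor the Appendix D follow-up column lists an examination. The cutoff is still not stated consistently.

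A reader might also infer that late cancers would always be judged unrelated, because every patient has had chemotherapy and a transplant. Section 11.1.7 does not say so. Its NO answer for another cause requires evidence of that cause, and its YES answer includes a known pattern of response to the drug.

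Finally, the plan promises no 5-year second-cancer rate, and a single arm of about 50 patients could not attribute a few late cancers to the drug. That is fair. It makes the follow-up part an improvement at low cost rather than the correction of an error. It does not excuse the exception in Section 11.3.7.

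**Conclusion.** The point holds. As written, Section 11.3.7 would undercount second primary malignancy, a risk the protocol names, within a secondary objective. The direction follows from the rule under either reading of the exception. The size cannot be estimated from the documents.

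The window is a secondary part of the point. Under Section 11.1.6.2 and footnote t, related-only reporting covers 62% of the time from first dose for a patient who completes the drug and stays progression-free to 5 years. With 2-year PFS of 76-80% and a constant hazard, it covers about 54-55% of person-time. These figures measure time without causality-independent recording. Reading them as the share of cancers missed would be wrong, because later cancers judged related are still reported. A fatal second cancer would also count as a PFS event (Section 9.1), although a late one judged unrelated would not be reported as an AE.

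**What to change.** 1. **Section 11.3.7:** delete the exception, so that every new primary cancer is recorded as an AE. Tabulate non-melanoma skin cancers separately, so that they do not obscure the other types.
2. **AE window:** reconcile Sections 6.5.11 and 11.1.6.1 with Section 11.1.6.2 and Appendix D footnote t, so that one period is stated throughout.
3. **Follow-up:** in Sections 6.4.6 and 11.1.6.2 and the Appendix D follow-up column, add that new primary cancers are recorded regardless of causality at each 3-monthly contact already scheduled, including the contact that ends follow-up. That last contact matters because Section 6.4.6 ends follow-up when another anticancer therapy starts, so treatment of a second cancer could itself close the record.
4. **Analysis:** add one summary table of new primary cancers in the Safety Analysis Set.

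For a patient who completes the drug and is followed to 5 years, causality-independent recording would rise from about 660 to 1,726 days. For 50 patients under the Step 4 assumptions, it would rise from about 82 to 184 person-years at 80% 2-year PFS, or from 80 to 174 at 76%.

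The cost is amendment wording, one eCRF question, one table, a few more AE records and a slightly less favourable reported second-cancer rate. One limit remains. Section 6.4.6 starts these contacts at 2 years and ends them at progression, withdrawal or new therapy, so complete collection in every patient to 5 years would need contacts that are not clearly scheduled. The change above does not ask for those.
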